5.4.2 Key secondary analysis

Not applicable.

5.5 Rule of exclusion criteria of analysis sets

Table 1 Protocol deviations that cause subjects to be excluded

Deviation ID	Description of Deviation	Exclusion from Analyses
I_01	No written informed consent	Excluded from all analyses
D_00	Not treated with any study medication	Excluded from FAS and SAF
O_VI0	No Post-baseline visit performed	Excluded from FAS

Table 2 Subject Classification

Analysis Set	PD ID that cause subjects to be excluded	Non-PD criteria that cause subjects to be excluded
ENR	I_01	
RAN	I_01	Not randomized
FAS	I_01, D_00, O_VI0	Not in RAN
SAF	I_01, D_00	

6 Reference

Not applicable.

7 Declaration of sponsor and clinical research organisation

Declaration by client:

[figure not shown]
This statistical analysis plan has been approved after review by

Client:

Digitally signed by [REDACTED]
DN: dc=com, dc=novartis, ou=people,
ou=PH, serialNumber=3168921,
cn=[REDACTED]
Reason: I am approving this document
Date: 2024.04.03 21:12:12 +02'00'

Date

Digitally signed by [REDACTED]
DN: dc=com, dc=novartis, ou=people,
ou=PH, serialNumber=1451277,
cn=[REDACTED]
Reason: I am approving this document
Date: 2024.04.03 11:20:21 +02'00'

[figure not shown]
Date

Declaration of clinical research organisation:

[figure not shown]
This statistical analysis was prepared based on the clinical study protocol (Amended Clinical Study Protocol, version 02 dated 03-NOV-2022) by

[REDACTED] :

Date

[REDACTED] (CRO Biometrician)

Date

[REDACTED] (CRO Biometrician)

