4.5 Risks and benefits

Ranibizumab and aflibercept (both approved inhibitors of VEGF-A) have consistently demonstrated efficacy in VEGF-driven retinal pathologies, including nAMD, with benefits outweighing the risks and are considered standard of care for treatment of nAMD patients.

In both phase 3 studies (HAWK and HARRIER) in nAMD, brolucizumab demonstrated non-inferiority to aflibercept in mean change in BCVA from baseline to week 48. These results were achieved while a majority of subjects on brolucizumab 6 mg – 56% in HAWK and 51% in HARRIER – were maintained on a q12w dosing interval following the loading phase through week 48, i.e. with a reduced treatment frequency compared to aflibercept. Brolucizumab safety was comparable to aflibercept, with the overall incidence of adverse events balanced across all treatment groups in both studies.

The lower probability of disease activity after the head-to-head comparison at week 16, the greater reduction in CSFT through week 48 and the lower proportion of patients with SRF and/or IRF at the majority of visits through week 48 for brolucizumab 6 mg versus aflibercept 2 mg in HAWK and HARRIER are anticipated to confer a longer duration of effect. This might translate into greater durability and longer injection intervals for brolucizumab 6 mg, with non-inferior efficacy. The potential superior anatomical results and a reduced treatment and monitoring visit frequency will provide benefit to subjects and caregivers/physicians. Further details of the known and potential risks and benefits associated with brolucizumab are presented in the Investigator's Brochure (IB).

Since until now only treatment-naive patients have been investigated with brolucizumab 6.0 mg treatment, this study will give insights on treatment response in pretreated patients. With the presumed longer lasting efficacy of brolucizumab the treatment burden also for pretreated patients might be reduced.

The risk to subjects in this trial may be minimized by compliance with the eligibility criteria and study procedures, as well as close clinical monitoring described in [Section 6.7.2](#), [Section 8.4.3](#) and [Section 10](#).

Women of child-bearing potential must be informed that taking the study treatment may involve unknown risks to the fetus if pregnancy were to occur during the study, and agree that in order

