In the “loading arm”, patients will receive three consecutive injections every 4 weeks at baseline, weeks 4 and 8, which should be at least 21 days apart, followed by an injection every 12 weeks. In the “non-loading arm”, patients will receive one initial injection followed by an injection every 12 weeks. For both study arms the assessment of disease activity will be performed 8 and 12 weeks after the previous injection. If disease activity is identified by the investigator for the first time at any visit after / from week 8 respectively, patients should stay on a q12w dosing, if the decline in BCVA is clinically non-significant (BCVA loss < 4 ETDRS letters) compared to the previous visit. If after / from week 8 BCVA-loss of ≥ 5 ETDRS letters appears compared to the previous visit or disease activity is identified for a second time based on the investigator’s judgment of visual and / or anatomic outcomes and signs of disease activity, patients must be assigned to q8w dosing. One attempt of interval re-extension from q8w to q12w treatment will be allowed based on the investigator’s judgement if no disease activity (DA) is detected during the subsequent visit(s). If the patient shows significant DA at any visit after the re-extension attempt, injection intervals will be fixed to q8w until the end of the study.

Patients who require injections more frequently than every 8 weeks after the loading phase (week 8, loading arm) or baseline (non-loading arm) will be discontinued from further study treatment.

3. Post-treatment follow-up period: Week 48 to week 52

For all patients, the last study assessment will be performed at week 52.

Patients withdrawn from the study prior to study completion will be asked to return for an early discontinuation visit (EOS / Visit 14), four weeks (± 7 days) following their last study visit.

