2.2 Analysis sets

The **Randomized Set** (RAS) consists of all randomized patients.

The **Full Analysis Set** (FAS) comprises all subjects who receive at least one IVT injection of the study treatment. The FAS will serve as the primary analysis set for all efficacy analyses. According to the intent to treat principle, subjects will be analyzed according to the treatment they have been assigned to during the randomization procedure.

The **Safety Set** includes all subjects who received at least one dose of study treatment. Subjects will be analyzed according to the study treatment received, where treatment received is defined as the actual treatment regime. If the subject took only one dose of study treatment, the subject will be analysed according to the randomized treatment regime.

Relevant protocol deviations and their potential impact on the analysis will be assessed and adequately documented / processed before database lock.

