2.7.2 Statistical hypothesis, model, and method of analysis

Secondary endpoints will be analyzed using adequate descriptive statistics, if not otherwise specified. Details on planned analyses are listed in the table below.

Table 2 Endpoints and statistical method

Endpoints for secondary objectives	Statistical method
1.Treatment interval	
1.1. Mean treatment interval (overall as well as per study group comparing treatment intervals from week 8 to week 52 in the study vs. 24 weeks to baseline prior to enrollment)	Descriptive analysis of injection intervals (weeks): Summary statistics (n,mean, SD, min, median, max) for - Mean treatment interval from week 8 to week 52 - Mean treatment interval within 24 weeks prior to baseline. - Last treatment interval under observation Box Plot for “last treatment interval under observation”. Stacked Bar Chart for patients on q8w and q12w by visit (last documented DAA).

1.2. Rate of patients (overall and per group) with prolonged interval compared to mean treatment interval in last 24 weeks to baseline prior to enrollment

- **Frequencies and percentages (n(%))** for total FAS and both treatment arms.

- **Logistic regression model**

Dependent variable: interval prolongation* (Y/N)

Factors:

- treatment arm
- baseline BCVA
- age

Odds-ratio, 95% CI and p-value.

Estimates for , non-loading arm, loading arm and difference (non-loading – loading).

* Prolongation is calculated by comparing the “mean treatment interval in last 24 weeks prior to first brolucizumab injection” (defined in section 2.3.2) with the time interval between the last two brolucizumab injections. Patients with only one injection in treatment period are calculated as non-responders (no interval prolongation).

2. Maintenance of q12w intervals

2.1. Comparison of proportions of patients maintained at a q12w interval at week 52 between the two arms

- **Frequencies and percentages (n(%))** for total FAS and both treatment arms.

- **Logistic regression model**

Dependent variable: “q12w” (Yes/No): “DAA maintained at q12w from baseline / upload to week 52”

Factors:

- treatment arm
- baseline BCVA
- age

Odds-ratio with 95% CI and p-value.

Patients who discontinued treatment prior to week 52 are calculated as non-responders.

2.2. Distributions of patients at q8w/q12w intervals from baseline to week 52

Descriptive statistics for treatment regimens:
Frequencies and percentages (n (%)) by visit

3. Functional Outcomes

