2.14 Interim analysis

There is no interim analysis planned.

3 Sample size calculation

Due to feasibility reasons, resulting in a substantial delay in recruitment, as described above, with Amendment 2 the recruitment will be prematurely discontinued. A final number of approximately 50 patients is expected to be recruited by the time of approval of the amendment.

As a consequence, all analyses will be performed and interpreted in a purely descriptive manner.

Based on an expected sample size of 25 patients per group, and an assumed common standard deviation of 13 letters, a precision in terms of the width of the respective 95% confidence interval for the difference in change from baseline of the visual acuity of +/- 7,21 can be achieved. Taking into account the current number of patients of (for 23 patients per group), the precision in terms of the half width of the 95% confidence interval would be 7,51.

4 Change to protocol specified analyses

The wording of secondary objective 2) was slightly changed to: "Comparison of proportions of patients maintained at a q12w interval **from baseline / upload to week 52**" instead of per protocol: "Comparison of proportions of patients maintained at a q12w interval **at week 52**".

5 Appendix

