5.4 Statistical models

5.4.1 Primary analysis

1) SAS-Code for **mixed model for repeated measures (MMRM)**:

Estimates for the primary objective ("Mean change in BCVA from baseline to mean of visits at week 40 to week 52 (Visit 11 to 14)") and the secondary objective ("Mean change in BCVA from baseline to mean of visits at week 16 to week 28 (Visit 5 to 8)") in one single model:

```
proc mixed alpha=0.1;
  where fasfl=Y and trteyen=1;
  where 2 le avisitn le 14;
  class subjid trtan avisitn;
  model chg = base age trtan avisitn trtan*avisitn /ddfm=kr;
  repeated avisitn / sub = subjid type = un;
  lsmeans trtan*avisitn /slice = avisitn cl ;
  estimate 'Treatment difference averaged over week 40 to week 52'
    trtan -1 1
    trtan * avisitn
      0 0 0 0 0 0 0 0 -0.25 -0.25 -0.25 -0.25
      0 0 0 0 0 0 0 0 0.25 0.25 0.25 0.25/cl;
  estimate 'Treatment difference averaged over week 16 to week 28'
    trtan -1 1
    trtan * avisitn
      0 0 0 -0.25 -0.25 -0.25 -0.25 0 0 0 0 0 0
      0 0 0 0.25 0.25 0.25 0.25 0 0 0 0 0 0/cl;
run;
```

3) SAS-Code for **logistic regression** model:

- Secondary endpoint: "rate of patients (overall and per treatment arm) with prolonged interval (*intlong*) compared to mean treatment interval in last 24 weeks prior to enrollment"

```
proc logistic descending alpha=0.05;
  where fasfl=Y;
  class trtan;
  model intlong = base age trtan;
run;
```

- Secondary endpoint: "proportions of patients maintained at a q12w interval from baseline / upload to week 52"

```
proc logistic descending alpha=0.05;
  where fasfl=Y;
  class trtan;
  model q12w = base age trtan;
run;
```

where 'maintained at a q12w interval' (q12w = Yes) is defined as DAA = q12w in all visits AND no treatment discontinuation.

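### SAP 5.5 drops treated patients with no post-baseline visit from the FAS, contrary to SAP 2.2 and protocol 12.1, and SAP Section 4 does not declare it

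*SAP*

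**What the plan says.** - **FAS definition.** SAP 2.2 says that the FAS "comprises all subjects who receive at least one IVT injection of the study treatment". Protocol 12.1 uses the same definition. Neither asks for a post-baseline visit, and both make the FAS the primary set for efficacy and invoke intent to treat.
- **Exclusion tables.** SAP 5.5, Table 1, lists deviation O_VI0, "No Post-baseline visit performed", with the consequence that the patient leaves the FAS. Table 2 repeats O_VI0 in the FAS row. It is absent from the Safety Set row.
- **Declared changes.** SAP Section 4 has one entry: "The wording of secondary objective 2) was slightly changed to", followed by the new wording. It says nothing about the FAS.
- **Scoring of patients who stop early.** In SAP 2.7.2, for interval prolongation: "Patients with only one injection in treatment period are calculated as non-responders". For q12w maintenance: "Patients who discontinued treatment prior to week 52 are calculated as non-responders". SAP 5.4.1 defines maintenance as "DAA = q12w in all visits AND no treatment discontinuation".
- **Models.** Both logistic regressions in SAP 5.4.1 are restricted to the FAS flag (`fasfl=Y`).

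**The concern.** The SAP gives two different answers to who is in the FAS. A patient injected on day 1 who never attends again is in the set under SAP 2.2 and out of it under SAP 5.5. The programmer will most likely work from the exclusion tables, while a reader of the report will rely on the definition in the protocol.

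The difference matters because these patients are not neutral for two of the secondary endpoints. The SAP has already decided how to score a patient with a single injection or an early stop, namely as a failure. An exclusion that reaches only such patients cancels that decision for the clearest cases. Whether a patient returns is also known only after randomization, in a trial where treatment is open to patients, site staff and the trial team (protocol 6.4). At stake are the denominators of the interval-prolongation and q12w-maintenance rates, and the two odds ratios built on them.

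**Working it through.** **Step 1. Whom O_VI0 reaches.** Injections are given at, or within days after, study visits (protocol Section 3). A patient with no post-baseline visit therefore has the day-1 injection only and has stopped treatment before week 52. D_00 already covers patients never treated, so O_VI0 adds exactly the group that was treated once and never seen again.

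**Step 2. How the SAP scores that group.** With one injection, the patient is a non-responder for prolongation. Having stopped treatment early, the patient is a non-responder for q12w maintenance. Under SAP 2.2 such a patient adds 0 to the numerator and 1 to the denominator of each rate. Under SAP 5.5 the patient adds nothing to either.

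**Step 3. Effect on an arm's rate.** The plan gives no expected value for either rate, so there is no plan figure to reproduce for these endpoints. The 25 per arm comes from protocol 12.8.1 and SAP Section 3. The precision stated there is reproduced by 1.96 × 13 × sqrt(2/25) = 7.21 letters. It concerns the primary endpoint and serves here only as the source of the arm size.

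With x responders among n patients and k excluded, the rate rises by x/(n − k) − x/n = xk/[n(n − k)]. This is never negative, and it is zero only if x = 0. The responder counts are assumed. The middle ones lie near the q12w rates the protocol cites from the two phase 3 trials, "56% in HAWK and 51% in HARRIER", which serve as an anchor only.

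| Responders x | All 25 kept | One excluded | Two excluded |
|---|---|---|---|
| 5 | 20.0% | 5/24 = 20.8% | 5/23 = 21.7% |
| 13 | 52.0% | 13/24 = 54.2% | 13/23 = 56.5% |
| 14 | 56.0% | 14/24 = 58.3% | 14/23 = 60.9% |
| 20 | 80.0% | 20/24 = 83.3% | 20/23 = 87.0% |

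**Step 4. Effect on the comparison.** Take 13/25 in both arms, so the crude odds ratio is 1.00.

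- One excluded in the numerator arm: (13/11)/(13/12) = 1.09. Two: (13/10)/(13/12) = 1.20.
- The same losses in the other arm give the reciprocals: 1/1.09 = 0.92 and 1/1.20 = 0.83.
- One lost from each arm: (13/11)/(13/11) = 1.00.
- 95% interval at 1.00: exp(±1.96 × sqrt(2/13 + 2/12)) = 0.33 to 3.03.

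These are crude odds ratios; the SAP's model also adjusts for baseline BCVA and age.

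**Step 5. Effect on the primary analysis.** The mixed model in SAP 5.4.1 uses change from baseline at Visits 2 to 14. A patient with no post-baseline visit has no such record and contributes nothing, whether flagged into the FAS or not. In a simulated data set of 50 patients, one of them without post-baseline values, a random-intercept version of the model (simpler than the SAP's unstructured covariance) gave the same treatment coefficient both ways, from the same 637 records.

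**The case against.** The strongest reply is that little depends on this. O_VI0 needs a patient who is injected once and never attends again, not even for a closing visit. There may be none among about 50 patients. All analyses are declared descriptive, the primary result does not move, and the odds-ratio shifts in Step 4 are small beside an interval of 0.33 to 3.03. Requiring a post-baseline observation is also a familiar convention. Protocol 12.1 and SAP 2.2 further say that relevant deviations will be assessed and documented before database lock, so any case would be visible.

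Most of this stands, and it limits the weight of the point. Two parts do not settle it. The sentence on deviations promises assessment and documentation; it does not authorise removal from the FAS. The convention suits an endpoint that cannot be computed without a later measurement, but here the SAP says how to score these patients without one.

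A reader might infer that the exclusion biases the comparison towards one regimen. The documents do not support that. Only the rate within the affected arm has a fixed direction. The odds ratio can rise, fall or stay put, depending on which arm loses patients, and nothing in the plan indicates which arm that would be.

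**Conclusion.** The inconsistency is certain from the text: SAP 5.5 narrows the FAS that SAP 2.2 and protocol 12.1 define, and Section 4 does not say so. Following 5.5 removes only patients whom the SAP counts as failures. At 25 per arm and 52% responders (an assumed count), each arm's rate rises by 2.2 points for one exclusion and 4.5 for two. For one exclusion the rise is 0.8 to 3.3 points over 5 to 20 responders. The effect on the odds ratio has no fixed direction and is small against its uncertainty. The primary estimate does not change. The number of affected patients is not in the documents and may be zero. This should be corrected, with modest weight.

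A reader might go further and infer a fault in how early leavers are handled at week 52, because SAP 1.1 says that withdrawn patients are "asked to return for an early discontinuation visit (EOS / Visit 14), four weeks" after their last visit, and SAP 5.4.1 treats Visit 14 as week 52. The documents do not show that. No passage says that an early closing visit is analysed as week 52, the derivation of the analysis visit number is not shown, and protocol Section 8 ties visits to day 1 with windows. That inference is not part of this point.

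**What to change.** Delete O_VI0 from the FAS exclusions in both SAP 5.5 tables. The FAS then matches SAP 2.2 and protocol 12.1, and treated patients who never return count as non-responders for the two logistic endpoints, as SAP 2.7.2 intends.

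Keeping O_VI0 and declaring it in SAP 2.2 and Section 4 would remove the contradiction, but it would still take failures out of both rates. Deletion is the better repair.

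The cost is two table entries. No model code changes and the primary analysis is untouched. The two rates may come out slightly less favourable if any such patient exists.
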